Protocol March 7, 2018

Androgen Excess as a Cause for Adipogenic Dysfunction in PCOS Women

NIH Prime Award No 1U54HDO71836-01A1, Subaward #9009028 UCLA

NCT01889199

UCLA IRB #12-001780

Principal Investigator

[name] Chief, Division of Reproductive Endocrinology and Infertility UCLA Department of Obstetrics and Gynecology

Co-Principal Investigator

[name] Division of Reproductive Endocrinology and Infertility UCLA Department of Obstetrics and Gynecology

Co-Investigators

[name] UCLA Department of Plastic Surgery

[name] UCLA Department of Radiological Sciences

[name] [name] UCLA Department of Radiological Sciences

Collaborating Investigator

[name] Department of Obstetrics and Gynecology University of Wisconsin, Madison Revised 3-7-18 UCLA IRB #12-001780 Page 2 of 27

LAY SUMMARY

The purpose of this research study is to collect specimen samples and study medical information from women with Polycystic Ovary Syndrome (PCOS) and women without PCOS. The goal is to learn more about the changes that take place in the body that result in PCOS.

We anticipate that 70 women will be enrolled in this study (20 without PCOS and 50 with PCOS). All patients will undergo a physical exam, blood tests, and transvaginal ultrasound of their ovaries. If they meet the criteria for this study, they will then undergo additional blood tests, removal of abdominal fat, transvaginal ovarian ultrasound, MRI, DXA scan, frequently-sampled intravenous glucose tolerance test (FSIGT), follicle stimulating hormone stimulation test, and Quality of Life surveys. The women without PCOS will be complete the study at this point.

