Subjects and clinical assessment: We will recruit subjects with the intention of enrolling 90 women - 70 lean (18.5-25 kg/M2) PCOS subjects and 20 age- and BMI-matched controls with the assumption that there will be dropouts such that 36 women with PCOS and 12 controls will complete the study. Subjects will complete a standardized questionnaire emphasizing menstrual dating, abnormal hair growth and acne. The questionnaire also will annotate age, smoking status, medications, surgical history and family histories of excess hair growth in female relatives and of diabetes in parents or siblings for exclusion criteria and for inclusion of some basic traits as covariates. Subjects also will undergo a physical examination; hirsutism will be scored by the modified Ferriman-Gallwey (mFG) method. Transvaginal sonography (TVUS) will be performed to determine the presence or absence of polycystic ovaries by Rotterdam

Revised 3-7-18 UCLA IRB #12-001780 Page 5 of 27

criterion. A screening blood sample will be obtained for determinations of steroid hormones, TSH, and prolactin; biochemical hyperandrogenism will be defined as an elevated serum total or free T > 2 SD above the mean value. Non-Hispanic Caucasian women between the ages of 18 and 35 years will be recruited to avoid confounding differences as a function of race. PCOS patients will be diagnosed by 1990 NIH criteria. Controls will have regular menstrual cycles at 21 to 35 day intervals, a luteal phase progesterone (P4) level > 3 ng/mL, and no evidence of hirsutism, acne, alopecia, polycystic ovaries or endocrine dysfunction. Exclusion criteria are: present/past history of smoking during the past year, cancer, alcohol abuse, drug addiction, severe depression, or post traumatic stress; diabetes; uncontrolled hypertension (\geq 165/100); clinically significant hepatic or renal disease, or other major medical illness; signs or symptoms of infection; recent (within 30 days) use of an experimental device; recent (within 6 months) use of androgens, anabolic steroids or non-steroidal anti-inflammatory drugs; recent (within 3 months) use of hormonal agents (including birth control pills, Plan B, Mirena IUD, or insulin sensitizers); use of the drug warfarin; beta blockers; CYP active medications or herbs.

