iii). Body fat distribution: Total body DXA will measure abdominal fat (i.e., the area between the dome of the diaphragm [cephalad limit] and the top of the greater trochanter [caudal limit]). Total body DEXA images also will determine % body fat; fatfree body mass; total body, abdominal, and leg fat; and abdomen/leg fat mass ratio. The leg region is that area below the top of the greater trochanter. Multiple axial abdominal and pelvic MRI slices from the diaphragm to the pelvis will assess cross-sectional areas of SC abdominal and visceral fat.

iv). Ovarian testing:

a). Ovarian morphology: TVUS using a 4- to 8-mHz vaginal probe will be performed in the follicular phase in controls and during amenorrhea in PCOS women. Summed ovarian volume will be calculated. Antral follicle number, defined as the total follicle number (2-9 mm in diameter) of both ovaries, will be determined by 1 investigator ([name]). Polycystic ovaries will be defined by 12 or more follicles in each ovary measuring 2-9 mm in diameter, and/or increased ovarian volume (> 10 ml), with one such ovary sufficient to define PCO.

b). E2 response to recombinant human (rh)FSH. Blood samples will be drawn through an indwelling iv catheter at -90, -60, -30 minutes and time 0 as well as 0.5, 1, 1.5, 2, 3, 4, 6, 8, 10, 12, 16, 20, and 24 h after 150 U rhFSH injection (112). The E2 response to rhFSH will be assessed before and after adjusting for numbers of TVUS-detected ovarian antral follicles.

Aim 2. Examine effect of flutamide in lean PCOS women on SC abdominal adipogenesis, visceral adipose content and ovarian folliculogenesis.

Per amendment #29, we are requesting permission to change the randomization strategy since all PCOS subjects enrolled thus far have been non-insulin resistant

Revised 3-7-18 UCLA IRB #12-001780 Page 7 of 27

based upon the results of the Frequently Sampled Intravenous Glucose Tolerance Test. Therefore, the need to stratify the PCOS subjects into two groups (i.e. insulin resistant versus non-insulin resistant) is unnecessary. All PCOS subjects recruited will now be randomized to study drug versus placebo based upon non-insulin resistant status. Of note, the control subjects are not randomized since they do not receive study drug or placebo.

Adipogenic studies: All adipogenic studies performed at study initiation will be repeated at the end of the 6 - 28 day cycles of flutamide vs. placebo intervention in PCOS women.

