Per amendment #42, epigenetic studies (RNA sequencing, DNA Methylation, and Assay for Transposase Accessible Chromatin Sequencing) on existing fat cell samples will be conducted at UCLA.

INCLUSION CRITERIA

Caucasian and Non-Hispanic women between the ages of 18 to 35 years.

Groups will be: 12 lean controls (Aim 1); 36 age- and BMI-matched PCOS women randomized to flutamide vs. placebo for 6 months (Aims 1 and 2).

i) Lean patients with PCOS: 36 subjects with PCOS (defined by 1990 NIH criteria [all Aims]), BMI 18.5-25 kg/m2. This BMI range is defined as normal and has been chosen to examine underlying mechanisms of PCOS-related androgen excess in the genesis of adipogenic and ovarian dysfunction, independent of obesity. Excessive course hair on upper lip, chin, chest, upper back, lower back, upper abdomen, lower abdomen, arm and/or thigh.

ii) Lean control women: 12 healthy subjects, BMI 18.5-25 kg/m2. Controls will have regular menstrual cycles, and no evidence of hirsutism, acne, alopecia, polycystic ovaries, and/or endocrine dysfunction. This BMI range has been chosen to match that of the PCOS group.

Up to 70 lean PCOS patients and 20 lean controls will be recruited, for a total of 90 study participants over a 5-year interval, accounting for a 20% rate of patient drop-out or insufficient adipose procurement. Participants must be fluent in English.

EXCLUSION CRITERIA

Exclusion criteria for study participation are: present or past history of smoking within past 1 year, cancer, alcohol abuse within past 5 years, drug addiction within past 5 years, severe depression within past 5 years, or post traumatic stress disorder within

Revised 3-7-18 UCLA IRB #12-001780 Page 10 of 27

past 5 years; diabetes; uncontrolled hypertension (≥ 165/100); clinically significant hepatic or renal disease, or other major medical illness; recent (within 3 months) use of androgens, anabolic steroids or hormonal agents (including birth control pills or insulin sensitizers), Mirena IUD, or Plan B contraception. These exclusion criteria are chosen to avoid effects from medical conditions, environmental factors or exogenous agents. Women taking the drug warfarin, beta blockers, CYP active medications, or herbs will be excluded.

Since this study involves MRI testing, women with pacemakers, metal implants, or claustrophobia will be excluded.

The screener will assess the participants response to establish if depression or drug use exclude participation in this study.

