We will use one-way factorial analysis of variance (ANOVA) methods to compare continuous outcomes including hormone levels; adipocyte size, lipid content and glycerol release; numbers of ASCs and preadipocytes; mRNA levels. If data are not normally distributed on any scale, we will carry out nonparametric ANOVA.

Our previous comparison of cFOS gene expression in PCOS women vs. controls showed an increase in Δ Ct (6.0 ± 1.4). Based on this, we hypothesize that the mean difference between controls and IR PCOS is 1.7 SD units. Assuming this, a sample size of 8/group (IR vs. non-IR PCOS) provides over 80% power using the usual two-sided p < 0.05.

We also will compare all outcomes before vs. after 6 months of placebo or flutamide treatment controlling for IR status, using either the parametric paired t test or non-parametric Wilcoxon signed rank test. Insulin action and sensitivity will be assessed by calculating a Matsuda Index from blood glucose and insulin levels during the oral glucose tolerance test. Ovarian estradiol sensitivity to FSH will be calculated from the 24-hr area-under-the-curve (AUC) serum estradiol response to FSH infusion.

Based on our in vitro data, we observed a mean 0.17 log scale change in Δ Ct PPAR γ (SD=0.26 log units) after treatment with T + Flutamide vs. T alone. A sample size of 14 (7 non-IR, 7 IR) provides more than 80% power for the IR adjusted mean change.

REFERENCES

3. 2004. Revised 2003 consensus on diagnostic criteria and long-term health risks related to polycystic ovary syndrome. Fertil Steril 81(1):19-25.

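### The Aim 2 power claim of more than 80% with 14 women is about 62% on its own inputs, and its 7 + 7 insulin-resistance split is obsolete

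*Combined protocol and SAP*

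**What the plan says.** The Statistical Considerations section plans to compare every outcome before and after six months of placebo or flutamide, controlling for insulin-resistance (IR) status, "using either the parametric paired t test or non-parametric Wilcoxon signed rank test". The Aim 2 power statement that follows rests on in vitro data: a mean change of 0.17 on the log scale in PPARγ ΔCt ("SD=0.26 log units) after treatment with T + Flutamide vs. T alone"). It concludes: "A sample size of 14 (7 non-IR, 7 IR) provides more than 80% power for the IR adjusted mean change". That sentence gives no significance level. The Aim 1 power sentence earlier in the section does, "using the usual two-sided p < 0.05".

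Under Aim 2 in Research Design and Methods, amendment #29 reports that all PCOS women enrolled so far are non-insulin resistant, that "the need to stratify the PCOS subjects into two groups (i.e. insulin resistant versus non-insulin resistant) is unnecessary", and that randomization now proceeds on non-IR status.

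The PCOS numbers differ by section. The Lay Summary expects 50 women with PCOS. The Aim 1 methods intend to enrol 70, "with the assumption that there will be dropouts such that 36 women with PCOS and 12 controls will complete the study". The Inclusion Criteria say "Up to 70 lean PCOS patients and 20 lean controls will be recruited", allowing for 20% loss to drop-out or insufficient tissue, and also give a PCOS group size of 36.

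**The concern.** A standardized change of about 0.65 is moderate, and 14 pairs are few for detecting it. A claim of more than 80% looks too high before any calculation. The claim also depends on an analysis adjusted for IR in a sample half IR and half non-IR, and the protocol itself says it is not recruiting such a sample.

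The documents contain no other power statement for Aim 2, the randomized part of the study. Taken at face value, it tells a reader that a null within-arm PPARγ change had less than a 20% chance of arising if the assumed effect were real. On the stated inputs that chance is about 38% (100 − 61.9).

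**Working it through.** **Inputs**

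- Mean change 0.17, SD 0.26 and n = 14: the Aim 2 power statement. The SD is attached to the mean change, so it is read as the SD of the change.
- Paired t test, or Wilcoxon signed rank: the paragraph on before-after comparisons.
- Two-sided 0.05: the Aim 1 power sentence, which calls it usual. Carrying it to Aim 2 is an inference, though a natural one.
- 36 PCOS completers: Aim 1 methods and Inclusion Criteria. The split of 18 per arm is an assumption.

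**Attempt to reproduce the plan's figure**

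Standardized change: d = 0.17/0.26 = 0.654.

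Non-centrality: d√n = 0.654 × √14 = 2.446.

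Critical value: t(0.975, 13 df) = 2.160.

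Power is the probability that a non-central t variable with 13 df and non-centrality 2.446 falls outside ±2.160. This is **61.9%**. Spending one degree of freedom on IR status (12 df) gives 61.3%. The figure of more than 80% is not reproduced.

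**Power by number of women, two-sided paired t**

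| Women in the arm | Source | Power |
|---|---|---|
| 14 | as stated | 61.9% |
| 18 | 36 completers, 1:1 assumed | 74.4% |
| 20 | 50 × 0.8 = 40 completers, 1:1 assumed | 79.2% |
| 21 | smallest n reaching 80% | 81.3% |
| 28 | 70 × 0.8 = 56 completers, 1:1 assumed | 91.5% |

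The counts 40 and 56 are derived here from the enrolment figures and the 20% loss. The documents state only 36. Going from 70 to 36 is a loss of 34/70 = 49%, which does not match 20%.

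**Could another convention give more than 80% at n = 14?**

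| Variant | Power |
|---|---|
| Wilcoxon signed rank, two-sided (20,000 normal simulations) | about 60% |
| Two-sided t, least favourable rounding (0.165/0.265) | 57.8% |
| Two-sided t, most favourable rounding (0.175/0.255) | 66.1% |
| Two-sided normal approximation | 68.7% |
| One-sided t | 74.9% |
| One-sided normal approximation | 78.9% |

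None exceeds 80% with the inputs as printed.

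**What would be needed at n = 14**

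- 80% power with 13 df needs d = 0.810, so an SD of 0.17/0.810 = 0.210. IR adjustment would have to remove 1 − (0.210/0.26)² ≈ 35% of the variance. No such figure is given, and the adjustment has no role if every woman is non-IR.
- If 0.26 were the SD within each condition, the SD of the change would be 0.26√(2(1 − ρ)). Setting this to 0.210 gives ρ = 1 − 0.210²/(2 × 0.26²) ≈ 0.67. No before-after correlation is stated.

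**Flutamide against placebo, for context**

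If the same 0.17 and 0.26 applied to the difference in change between arms, a two-sample t test with 18 per arm would have 47.9% power. The difference detectable with 80% power would be 0.961 SD, or 0.961 × 0.26 = 0.25 log units. The documents do not supply inputs for this comparison, so it is illustrative only.

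**The case against.** The strongest reply is that the Aim 2 sentence states neither a level nor sidedness, and does not say whether 0.26 is an SD of change, a per-condition SD or an adjusted SD. The 62% therefore depends on filling gaps. A one-sided normal approximation gives 78.9%, and with the most favourable rounding of both inputs it gives 82.2%. Part of this stands: the level is borrowed from the Aim 1 sentence, and the SD reading should be confirmed by the sponsor. It does not rescue the claim. Passing 80% that way needs a one-sided test against the section's own two-sided level, a normal approximation with 14 observations, and favourable rounding of both inputs.

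A second reply is that the study does not stop at 14. With 36 completers the shortfall is about 6 points, no primary endpoint is named, and PPARγ is one of many mechanistic outcomes. That is fair as to consequence: the fault lies in the written justification, and how urgently it must be corrected can be argued. But 36 is the only completer count stated, and on it the within-arm power is still below 80% under a 1:1 split.

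A third reply is that the scenarios of 40 and 56 completers are the reviewer's own. They are, and they are labelled so. They show that whether 80% is reached depends on enrolment and loss figures that the protocol has not reconciled.

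**Conclusion.** The concern holds. With a mean change of 0.17, SD of the change 0.26, 14 women and a two-sided 0.05 paired t test, power is 62%, about 18 points below the stated minimum. At 18 women per arm it is 74%, and 21 per arm are needed for 80%. The result rests on reading 0.26 as the SD of the change and on applying the section's two-sided level to Aim 2; the per-arm figures also assume 1:1 allocation. Separately, the 7 + 7 split describes a sample that amendment #29 says is not being recruited.

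**What to change.** Replace the sentence with wording such as: *Taking these in vitro values (mean change 0.17, SD of the change 0.26 log units) and a two-sided 0.05 paired t test, 14 women give 62% power and 18 women (36 completers, assuming 1:1) give 74% power for the within-arm change.* In addition:

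- Delete the 7 non-IR and 7 IR breakdown. In the same edit, bring the remaining IR wording into line with amendment #29: control for IR status and the IR versus non-IR groups in Statistical Considerations, and the IR stratification in the Lay Summary.
- If 0.26 is a per-condition SD, say so and give the before-after correlation that was used.
- State the allocation ratio.
- Reconcile the PCOS counts (50 in the Lay Summary; 70 recruited, 36 completers and 20% loss elsewhere) so that the power figure rests on one number.
- Optionally, report the flutamide-versus-placebo comparison at 18 per arm (48% power; 0.25 log units detectable with 80% power), labelled as assuming the same effect and SD for the difference in change.

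The cost is wording only. No enrolment or procedure changes; the stated power becomes less favourable.

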BACKGROUND AND SIGNIFICANCE

Polycystic ovary syndrome (PCOS): PCOS, a common endocrinopathy affecting 6–10% of women, manifests by hyperandrogenism, ovulatory dysfunction and polycystic ovaries (PCO) in its complete phenotype. Abdominal adiposity occurs frequently in PCOS women vs. controls, including some, but not all, nonobese individuals. Consequently, the estimated prevalence of MBS in PCOS is 33-47%, about 2-3 times higher than that of age-matched controls.

Interplay between adipose function and androgen excess: In PCOS, intrinsic defects combine with endocrine factors to impair insulin sensitivity and induce adipocyte insulin resistance (IR). Conversely, physiological androgen administration to women induces IR. In PCOS women, therefore, androgen excess could decrease numbers of SC abdominal adipocytes and reduce capacity of this adipose to safely store fat. Thus, if energy intake exceeds this capacity, SC abdominal adipocytes would likely overfill with lipid to promote ectopic lipid deposition. We hypothesize that PCOS-related hyperandrogenism decreases adipogenic differentiation and increases adipocyte lipid content in a constrained SC abdominal adipose, inducing lipotoxicity, IR and ovulatory dysfunction.

Therefore, reducing PCOS-related androgen excess could improve SC abdominal adipogenic function and ovarian folliculogenesis, reducing use of ovulation-inducing agents in PCOS women wishing to conceive, and risks of multiple pregnancy.

Effect of flutamide on PCOS: Administration of flutamide, a nonsteroidal anti-androgen, to PCOS women lowers circulating androgen and triglycerides levels. Flutamide also restores ovulation in some, but not all, PCOS women. We will systematically compare SC abdominal adipogenesis, circulating adipogenic markers and SC abdominal as well as visceral (omental plus mesenteric) adipose content of lean PCOS women randomized to 6-month low-dose flutamide vs. placebo to determine how differences in key variables affect ovarian function and morphology, as well as in vivo E2 responsiveness to FSH.

We also are able to quantify SC abdominal and visceral adipose content by magnetic resonance imaging (MRI), as performed by [name]. Finally low-dose flutamide vs, placebo administration to lean PCOS women will discover novel molecular and biochemical markers that predict efficacy of androgen blockade in restoring adipogenic and ovarian function.

AIMS AND OBJECTIVES

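### The Aim 2 power figure is for a mean change in 14 women; none is given for the randomized flutamide-placebo comparison, which has about 48% power at 36 completers if 0.26 is the SD of change

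*Combined protocol and SAP*

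**What the plan says.** Statistical Considerations gives one calculation for the treatment period. Its input is in vitro: "we observed a mean 0.17 log scale change in Δ Ct PPAR γ (SD=0.26 log units) after treatment with T + Flutamide vs. T alone". Its conclusion is "A sample size of 14 (7 non-IR, 7 IR) provides more than 80% power for the IR adjusted mean change". That sentence names no test, alpha or sidedness. The cFOS calculation earlier in the section, which is for a comparison of groups, "provides over 80% power using the usual two-sided p < 0.05".

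The analysis described for the treatment period is within-woman: "We also will compare all outcomes before vs. after 6 months of placebo or flutamide treatment controlling for IR status", by paired t test or Wilcoxon signed rank test. One-way ANOVA is named in general for continuous outcomes, but it is not tied to a comparison of change between the two arms.

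The design is parallel-group. Background and Significance says the study will compare "adipose content of lean PCOS women randomized to 6-month low-dose flutamide vs. placebo to determine how differences in key variables affect ovarian function and morphology". Inclusion Criteria lists "36 age- and BMI-matched PCOS women randomized to flutamide vs. placebo for 6 months (Aims 1 and 2". The Subjects and clinical assessment paragraph under Aim 1 expects 36 women with PCOS to complete. Under Aim 2, amendment #29 drops stratification by insulin resistance (IR) because every PCOS woman enrolled up to then was non-insulin resistant. No allocation ratio is stated.

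**The concern.** The sizing and the design answer different questions. A single set of 14 women and a mean change describe how precisely one group's before-after change can be estimated. Randomization to placebo is there to support the difference in change between two groups of different women. With n women per arm, the variance of that difference is twice the variance of one arm's mean change.

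The effect input makes the gap plainer. The 0.17 is itself treated against untreated: testosterone plus flutamide against testosterone alone. Its closest counterpart in the trial is flutamide minus placebo, not after minus before on flutamide.

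Women in Aim 2 take study drug or placebo for six cycles and have two fat biopsies. The reader of the plan has no statement of what the resulting randomized comparison can detect, and the one power figure available describes something else.

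**Working it through.** **Inputs from the documents.** Mean change 0.17, SD 0.26 log units, 14 women, more than 80% power (Statistical Considerations); two-sided 0.05 (same section, cFOS calculation); 36 PCOS completers (Research Design and Methods, Aim 1).

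**Assumptions.** 1:1 allocation, so 18 per arm; 0.26 is the SD of change in both arms; mean change on placebo is zero, so that 0.17 is the between-arm difference.

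Standardized effect: d = 0.17/0.26 = 0.654. Power is from the noncentral t distribution unless noted.

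**Step 1: the plan's own figure.** For one group of n = 14, the noncentrality is d × √n = 0.654 × √14 = 2.45, with 13 df.

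| Reading of 14 | Power |
|---|---|
| Paired t, two-sided | 61.9% |
| Paired t, two-sided, one df spent on IR status | 61.3% |
| Normal approximation, two-sided | 68.7% |
| Paired t, one-sided | 74.9% |
| Normal approximation, one-sided | 78.9% |
| Two-sample t, two-sided, 14 per arm | 38.5% |
| Two-sample t, two-sided, 7 per arm | 20.3% |

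No reading with 0.26 as the SD of change exceeds 80%. Two-sided 80% would need 21 women in one group by t test, or 19 by normal approximation. The one-group readings come closest, which fits the wording but does not prove which formula was used.

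**Step 2: the randomized contrast.** For n per arm, the noncentrality is d/√(2/n). At n = 18 it is 0.654/√(2/18) = 1.96, with 34 df.

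- 18 per arm, two-sided: 47.9% (one-sided 60.9%; normal approximation, two-sided, 50.1%).
- 24 and 12 women, as an example of unequal allocation: 43.5%.
- Per-arm size for 80%: 38 by t test (37 by normal approximation).
- Smallest difference with 80% power at 18 per arm: 0.961 SD, and 0.961 × 0.26 = 0.25 log units.

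**Step 3: baseline-adjusted ANCOVA, 0.26 as the SD of change.** With equal variances before and after and pre-post correlation r, adjustment multiplies the change-score variance by (1 + r)/2 and costs one df. The documents give no r. At 18 per arm:

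| Assumed r | 0 | 0.3 | 0.5 | 0.7 | 0.9 |
|---|---|---|---|---|---|
| Power | 77% | 66% | 59% | 54% | 50% |

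**Step 4: the other reading of 0.26.** If it is the SD of a single measurement, the SD of change is 0.26 × √(2(1 − r)).

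| Assumed r | 0 | 0.5 | 0.7 | 0.8 |
|---|---|---|---|---|
| SD of change | 0.368 | 0.260 | 0.201 | 0.164 |
| Paired t, 14 women | 36% | 62% | 83% | 95% |
| Difference in change, 18 per arm | 27% | 48% | 69% | 85% |
| ANCOVA, 18 per arm | 48% | 59% | 76% | 89% |

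On this reading the printed figure can be reached, at r of about 0.7, but the between-arm power at that correlation is still below 80%.

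**The case against.** The strongest reply is that the power sentence is consistent with the analysis that its own section describes: paired, before against after. On that view the root gap is that no between-arm test of change is specified, and the sizing merely follows from it. This is a fair account of how the sentence arose. It does not supply a power for the comparison that the randomization was set up to make.

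A reader might infer that the plan claims more than 80% power for 36 women, or for flutamide against placebo. It does not. That figure is attached to 14 women and a mean change, and nothing is claimed for the other contrast. A reader might also state as fact that a one-group formula was used. The documents name none, and that remains an inference from the wording and the single total. The split of 14 might even have been meant per arm, but that gives 38.5%.

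It is also tempting to say that between-arm power is below 80% whatever is assumed. Step 4 shows otherwise: with 0.26 as a single-measurement SD and a correlation of 0.8, it is above 80%. The SD of change is the more natural reading, since 0.26 is printed beside a mean change, but the text does not settle it.

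Finally, one might predict that a non-significant result would be taken as evidence against the androgen hypothesis. The documents set no such decision rule, and PPARγ expression is not designated primary among the many Aim 2 outcomes.

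**Conclusion.** The concern holds in a limited form. The plan gives no power for the flutamide-placebo contrast, and its one treatment-period figure is not reproduced on the natural reading of its inputs: about 62%, against a stated figure of more than 80%, for a two-sided paired t test in 14 women. For the randomized difference in change, power is about 48% at 36 completers. That rests on 1:1 allocation, no mean placebo change, two-sided 0.05, and 0.26 as the SD of change in each arm. If 0.26 is a single-measurement SD, the range is 27% to 85% for correlations of 0 to 0.8. Both readings also carry an in vitro effect over to a six-month change in women, which is an assumption of the plan itself.

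The defect is a mismatch between sizing and design, plus a figure that does not reproduce. It does not show that the trial is the wrong size for all of its Aim 2 outcomes.

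**What to change.** Leave the sample size unchanged and replace the 14-woman sentence. Its IR split no longer matches amendment #29, so it needs rewriting in any case. The replacement should:

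- name the between-arm analysis of change and give its power at 36 completers;
- state the allocation ratio, and whether 0.26 is the SD of change or of a single measurement;
- if the analysis is baseline-adjusted ANCOVA, quote the power of that analysis: about 66%, 59% and 54% at assumed pre-post correlations of 0.3, 0.5 and 0.7, with 0.26 as the SD of change and 18 per arm;
- label the 48% and the detectable difference of about 0.25 log units as unadjusted t-test figures if they are shown, so that they are not taken for the power of the ANCOVA;
- commit to reporting the between-arm difference with its confidence interval.

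This takes a few sentences and adds no participants or procedures. The downside is a less favourable stated power.
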